70 To compare rejection episodes between LDLT and cadaveric transplant recipients.
- 71 1. To determine the incidence and severity of rejection episodes occurring within
72 one year after transplantation in recipients undergoing LDLT.
 - 73 2. To determine the incidence of steroid resistant rejection
 - 74 3. To determine the incidence of recurrent rejection occurring within 1 year after
75 transplantation

76 **3.3. Retrospective Hepatitis C Virus (HCV) Study**

77 **3.3.1. Primary Aim**

78 To determine if recurrent HCV disease at 1 yr (\pm 3 months), as observed histologically, is
79 more severe in patients undergoing LDLT as compared to cadaveric transplant.

80 **3.3.2. Secondary Aims**

81 To compare the rate of fibrosis progression (comparison of 1 yr. and most recent biopsy)
82 in LDLT and cadaveric transplant

83
84 To determine if cholestatic hepatitis in transplanted patients with HCV occurs at a higher
85 rate following LDLT as compared to cadaveric transplant controls.

86
87 To determine if rejection requiring treatment occurs at a higher rate in HCV patients who
88 undergo LDLT as compared to cadaveric transplant and to correlate this frequency of
89 treatment of rejection to aggressive recurrence of HCV as defined histologically.

90
91 To compare rate of graft loss secondary to HCV between LDLT recipients and cadaveric
92 recipients.

93 **3.4. Retrospective Hepatocellular Carcinoma (HCC) Study**

94 **3.4.1. Primary Aim**

95 To compare the outcomes for patients with HCC from the time of LDLT donor
96 evaluation for those receiving LDLT versus those not receiving LDLT. Outcomes
97 considered will include survival, hospitalizations, ablative treatments, and HCC
98 status/recurrence.

99 **3.4.2. Secondary Aim**

100 To compare the demographic characteristics, HCC stage, and outcome (patient survival
101 and cancer-free patient survival) in patients receiving LDLT or cadaveric transplant with
102 HCC as either a primary or secondary pre-transplant diagnosis (excluding incidental
103 tumors discovered at the time of transplant).

104 **3.5. SRTR Data Validation Study**

105 **3.5.1. Primary Aim**

106 To estimate the completeness and correctness of selected data elements submitted by the
107 transplant centers to the Organ Procurement and Transplantation Network (OPTN) and
108 subsequently transmitted to the Scientific Registry of Transplant Recipients (SRTR).

109 **3.5.2. Secondary Aims**

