146 approximately 800 patients were evaluated for LDLT at the 9 A2ALL transplant centers,
147 of which approximately 300 subsequently received LDLT and 500 did not. A subset of
148 this cohort with diagnoses of HCC at entry will also be used.

149

150 Other objectives regarding the post-transplant experience will compare LDLT to
151 contemporaneous cadaveric transplants beginning at the time of transplantation. The
152 analysis will control for center and date of transplantation as well as age, sex, disease
153 (HCC, cholestatic, HCV/HBV, alcoholic, other), and severity of illness (MELD score,
154 OPTN/UNOS status, CTP score). This comparison would involve approximately 300

155 LDLT recipients and approximately 250 cadaveric liver recipients. A subset of this
156 cohort with diagnoses of HCV at entry will also be used.

157

158 Living donor liver transplantation presents unique immunological setting that is
159 determined by three major variables that are different from the cadaveric setting, with the
160 potential to impact on short and long term graft and patient survival. First, regeneration
161 may be associated with different pattern of lymphocyte trafficking in and out the graft
162 resulting in a differential repopulation of the liver with donor cells, and unknown effects
163 on the extent of peripheral chimerism. Second, transplantation of a lobe from a living
164 donor is done under conditions allowing extremely short cold ischemic time (60 vs. 500
165 minutes), a variable that may affect the severity of the inflammatory and immune
166 response. Finally, it is estimated that 40% of LDLT are done in between genetically
167 related individuals, resulting in a potentially more favorable HLA matching.

168

169 Previous single center studies have suggested a reduced rate of rejection after adult to
170 adult LDLT. These observations should be validated by a carefully designed
171 retrospective analysis of rejection rate and severity in AALDLT recipients. The clinical
172 findings will determine the opportunities for appropriate clinical modifications in the
173 immunosuppression protocol for the prospective study, aiming at better outcomes for
174 graft rejection and recurrent disease. Moreover, they will set the stage for hypothesis-
175 driven experimental studies, aiming to determine pattern of immune response and the
176 potential development of favorable induction of tolerance.

177

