215 either respect. Sample records will be examined for completeness and ease of obtaining
216 information on all data elements before formal data collection begins.

217

218 a. At listing

219 Date of listing

220 DOB, sex, ethnicity (PHS categories)

221 Reasons for transplantation (list primary and secondary diseases)

222 MELD/UNOS status/CTP score at time of listing

223

224 b. Potential Donor

225 Date of each donor evaluation

226 Information on potential donor. Data collection on donors will largely be limited to
227 clinically significant pre- and post-donation events and a small amount of operative
228 information.

229 Donor outcome information

230 Reasons for not donating for those who do not donate

- 231 - Medical or psychological for donor
 - 232 o Medical condition (liver related vs. co-morbid medical conditions)
 - 233 o Anatomical
 - 234 o Size
 - 235 o Blood type
 - 236 o Psychological
- 237 - Donor declines/changes mind
- 238 - Recipient became too sick (or too well)
- 239 - Recipient received cadaveric transplant
- 240 - Other

241 Date of decision not to donate

- 242
243 c. Pre-transplant
244 Complications (treated ascites, treated SBP, variceal bleed, other GI bleeds requiring
245 transfusion, hepatorenal, hepatopulmonary, treated encephalopathy, TIPS,
246 portopulmonary hypertension, bony fracture [yes or no for each])
247 SBP Prophylaxis (yes/no)
248 Antiviral therapy (specific to HBV and HCV)
249 Changes in MELD, CTP, OPTN/UNOS status
250 Hospitalization admission and discharge date
251 Days in ICU
252 Death
253 Dates for each of these
254
255 d. Transplantation and beyond
256 Date of transplant
257 Selected intra-operative data
258 Hospitalization dates
259 Days in ICU
260 Retransplantation
261 Baseline immunosuppression regimen (tacrolimus, cyclosporine, or non-calcineurin
262 antagonist based); antibody induction (yes/no)
263 Treated rejection episodes within one year of transplant:
264 1. Date of rejection (treated rejection episodes separated by less than 22 days will be
265 considered the same event for analysis purposes).
266 2. Liver biopsy (when performed): Acute rejection severity as recorded in the
267 original pathology reading (mild, moderate, severe or undetermined)
268 3. Immunosuppression at transplant and at the initiation of anti-rejection therapy
269 4. Drugs used to treat rejection

270 **4.2.4. Sample Size and Power Calculations**

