437 test with $\alpha=0.05$. We will have 84% power to detect a difference in the probability of
438 graft loss at one year as large as 15% for LDLT versus 5% for cadaveric recipients.
439

440 **4.3.5. Statistical Analysis**

441 Fibrosis score will be analyzed using both ordinal and ordinary regression analyses, with
442 the LDLT versus cadaveric recipients as the variable of primary interest. Ordinal logistic
443 regression will be used to accommodate the ordinal nature of the fibrosis scale. Ordinary
444 regression analysis will supplement the ordinal analysis and will facilitate interpretation,
445 but does assume that the ordinal scale has roughly equal increments.

446 The proportions of patients with fibrosing cholestatic hepatitis and treated acute
447 rejection episodes will be analyzed using chi-square tests of equality of proportions
448 between LDLT and cadaveric groups. Logistic regression will be used to compare LDLT
449 versus cadaveric transplants, adjusted for other covariates. Finally, time to graft loss will
450 be analyzed using Cox regression, again comparing LDLT versus cadaveric recipients
451 and adjusting for other prognostic factors. Graft loss or death due to causes other than
452 HCV will be censored.

453 **4.4. Study of Hepatocellular Carcinoma**

454 **4.4.1. Study Methods**

455 LDLT recipients transplanted for HCC will be compared to HCC patients who had a
456 donor evaluated for possible LDLT but who did not receive a LDLT. The analysis will
457 adjust for cirrhosis etiology diagnosis, center, age, CTP/MELD score, use of ablation
458 pretransplant, and pre transplant ablation method (i.e. chemoembolization, RFA, etc.). In

459 addition, a comparative analysis of LDLT and cadaveric transplant patients with HCC
460 will be conducted.

461 **4.4.2. Participant Selection**

462 All right lobe LDLT patients age ≥ 18 whose donor was evaluated between January 1,
463 1998 and the start date of enrollment into the A2ALL-Cohort-01 Study at one of the
464 A2ALL transplant centers, with patient diagnosis either primary or secondary of cirrhosis
465 and HCC. Excluded subjects include any patient who was transplanted with a
466 preoperative diagnosis of HCC and cirrhosis where no HCC was found at explant
467 histology, and no prior ablation is recorded that may have caused complete necrosis of
468 tumor leading to pathologic disappearance. For the comparative study of LDLT and

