469 cadaveric transplant recipients, no supplemental contemporaneous cadaveric controls will
470 be used.

471 **4.4.3. Data Elements**

472 Maximum size and number by radiology pre-transplant and at transplant (explant)
473 Whether Milan criteria were met
474 Whether HCC was an incidental finding.
475 Date of diagnosis of disease recurrence post-transplant.
476 Number and type of HCC ablation procedures.

477 **4.4.4. Sample Size and Power Calculations**

478 We anticipate approximately 75 hepatocellular carcinomas among the ~ 300 LDLT cases,
479 and approximately 125 among the ~ 500 non-LDLT cases who were also evaluated for
480 LDLT. With 75 LDLT cases and 125 non-LDLT cases, we will have 90% power to
481 detect a difference in recurrence (or presence) of HCC of 10% versus 30%. Since
482 reduction of HCC in the non-LDLT group will be due to subsequent cadaveric
483 transplantation, this statistical test will compare the strategy of LDLT versus waiting for a
484 cadaveric transplant.

485 **4.4.5. Statistical Analysis**

486 Initial analysis of HCC will be primarily descriptive. The characteristics of HCC patients
487 described will include TNM explant pathologic stage, use of ablation pretransplant, and
488 pre transplant ablation method (i.e. chemoembolization, RFA, etc.). The proportion
489 recurring within one year will be presented, with 95% CI. Predictors of one-year
490 recurrence will be explored using logistic regression for patients with at least one year of
491 follow-up. The difference between recurrence (or presence) proportions for LDLT versus
492 non-LDLT patients will also be estimated using a 95% confidence interval. A comparison
493 of survival between these two groups will be performed using Cox regression, adjusted
494 for various prognostic covariates. A comparison of survival between LDLT and
495 cadaveric transplant recipients will also be performed.

496 **4.5. SRTR Data Validation Study**

497 *(This section does not apply to subjects who have the first living donor evaluated after*
498 *2/28/03)*

499 **4.5.1. Study Methods**

500 We will investigate records for all patients with LDLT, and a subset of patients not
501 receiving LDLT. These patients will be selected as needed to develop comparison
502 cohorts for the other Retrospective research aims. All patients to be studied as part of
503 any Retrospective cohort will be included in this validation study.

504

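### Ablation is an HCC outcome counted from donor evaluation, but its data element has no date, so procedures before and after time zero cannot be separated

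*Protocol*

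**What the plan says.** - **Aim (3.4.1).** The HCC primary aim is "To compare the outcomes for patients with HCC from the time of LDLT donor" evaluation, between patients who do and do not receive LDLT. The outcomes "considered will include survival, hospitalizations, ablative treatments, and HCC" status or recurrence.
- **Cohort (4.1).** The HCC patients are a subset of the donor-evaluation cohort: "this cohort with diagnoses of HCC at entry will also be used".
- **Data (4.4.3).** Ablation is listed as "Number and type of HCC ablation procedures". The line just above it, for recurrence, asks for a date: "Date of diagnosis of disease recurrence post-transplant".
- **Main-cohort data (4.2.3).** The pre-transplant list ends with "Dates for each of these", but ablation is not on that list.
- **Adjustment (4.4.1).** The comparison of LDLT recipients with HCC patients who had a donor evaluated but no LDLT will "adjust for cirrhosis etiology diagnosis, center, age, CTP/MELD score, use of ablation" before transplant, and the ablation method.
- **Analysis (4.4.5).** The patient characteristics "described will include TNM explant pathologic stage, use of ablation pretransplant, and" the method used. No analysis of ablation as an outcome is given.

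**The concern.** An outcome that runs from donor evaluation needs each event placed before or after that day. A number and a type cannot do this. In a cohort that already has HCC at entry, a total count may mix ablations given as management before time zero with those that belong to the comparison.

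The protocol's only boundary for ablation, transplant, is a different one, and it falls differently in the two groups. At stake are one of the four outcomes named in the HCC primary aim and the meaning of a covariate in the LDLT versus non-LDLT comparison.

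**Working it through.** The protocol states no figure for ablation, so there is none to reproduce. The only HCC power statement (4.4.4) concerns recurrence or presence of HCC. The check sets the sections against each other, followed by arithmetic on assumed rates to show what mixing can do.

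**1. Can the listed data be split at time zero?** Time zero is donor evaluation (3.4.1). Ablation before it is possible, because HCC is present at entry (4.1). The element gives a number and a type (4.4.3), and the dating instruction in 4.2.3 does not reach ablation. As listed, the answer is no. The protocol does ask for dates elsewhere: recurrence (4.4.3), treated rejection (4.2.3), and start and stop of antiviral therapy (4.3.3).

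**2. Does the pre-transplant boundary help?** It is used in 4.4.1 and 4.4.5. Each ablation falls in one of these periods:

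| Period | Role under 3.4.1 | Role under 4.4.1 |
|---|---|---|
| Before donor evaluation | not an outcome | covariate |
| Donor evaluation to transplant | outcome | covariate |
| After transplant | outcome | none |
| After donor evaluation, never transplanted | outcome | covariate |

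The second and fourth rows carry both roles. The fourth may be common among controls. In the Appendix A summary there are 862 candidates, of whom 335 received LDLT, leaving 862 − 335 = 527. Of these, 107 died or were removed from the list and 239 were still waiting: 107 + 239 = 346, and 346/527 = 66% had no transplant. This is for all candidates at the time of that report, not HCC patients alone.

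**3. What can mixing do to a ratio?** Let *b*₁ and *b*₀ be the mean ablations per patient after time zero (LDLT, non-LDLT), and *a*₁ and *a*₀ the means before it. The undated ratio is (*a*₁ + *b*₁)/(*a*₀ + *b*₀). This is a weighted average of the true ratio *b*₁/*b*₀ and the prior ratio *a*₁/*a*₀, with weight *a*₀/(*a*₀ + *b*₀) on the latter. All values below are assumed and none comes from the protocol. Take *b*₁ = 0.5 and *b*₀ = 1.0, a true ratio of 0.50.

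| *a*₁ | *a*₀ | Undated ratio |
|---|---|---|
| 0.5 | 0.5 | 1.0/1.5 = 0.67 |
| 1 | 1 | 1.5/2.0 = 0.75 |
| 2 | 2 | 2.5/3.0 = 0.83 |
| 0.5 | 2 | 1.0/3.0 = 0.33 |
| 2 | 0.5 | 2.5/1.5 = 1.67 |

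Equal prior means pull the ratio toward 1. Unequal ones can exaggerate it (0.33) or reverse it (1.67). With equal prior means the difference in means is unchanged, at 0.5 per patient.

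**The case against.** The strongest reply is that 4.4.3 is a short topic list, not a case report form. Section 8 places element definitions in a Manual of Operations that is not at hand and may ask for dates. Sections 4.4.1, 4.4.2 and 4.4.5 already need ablation placed relative to transplant, so some timing is implied. Section 4.7.3 collects admission and discharge dates and major inpatient interventions, which could date some ablations. The study is chart review, so charts can be queried again while links are kept. Ablation also has no power statement, and the initial HCC analysis is described as mainly descriptive.

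Much of this stands as a limit on the point. A reader might infer that dates will never be available and that the outcome cannot be rescued; the protocol does not support that. A reader might also infer that ablations before time zero are counted as outcomes. No section says so: there is no counting rule and no ablation outcome analysis.

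It does not remove the point. Timing relative to transplant is not timing relative to donor evaluation. The inpatient data do not name ablation and would miss outpatient procedures. Under 5.1.1, identifiers are to be destroyed for subjects who have died, cannot be located or decline the prospective study, so a later return to charts is time-limited and hardest where it relates to outcome. An analysis plan cannot supply a date that was not abstracted.

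**Conclusion.** The point holds as an inconsistency between an aim and its data element. Followed as written, 4.4.3 gives a count that cannot be divided at donor evaluation, and 4.4.1 makes the same procedures both outcome and covariate between donor evaluation and transplant, or throughout follow-up in controls never transplanted.

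The size is unknown. A reader might infer that the contrast is necessarily diluted toward equality, or is likely to reverse. Neither follows: dilution of a ratio requires similar prior counts in the two groups, reversal requires a sufficiently large excess in one, and the protocol gives no ablation frequency for either. The illustrative ratios show only that mixing can matter.

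The conclusion assumes that no document outside the protocol already requires a date for each ablation. It concerns one of four named HCC outcomes and one adjustment covariate; the measurement of survival itself is not in question. It should be corrected before abstraction, when the change is cheap.

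**What to change.** 1. In 4.4.3, replace the number and type of ablations with the date and type of each HCC ablation procedure. The number then follows.
2. For 3.4.1, state that only ablations after donor evaluation count as the outcome, over follow-up from donor evaluation to death or last follow-up in both groups. Follow-up should not stop at transplant: that would leave LDLT recipients with only their time before LDLT, in a comparison that 4.4.4 describes as LDLT against waiting for a cadaveric organ.
3. In 4.4.1, for the comparison that starts at donor evaluation, adjust only for ablations before donor evaluation. Pre-transplant ablation may remain a covariate in the comparison of LDLT with cadaveric recipients from transplant.

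The cost is one date field per procedure in charts that are already being read for type, for about 75 + 125 = 200 HCC patients (4.4.4), and slightly more abstraction time.

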271 We will compare the survival experience between those receiving a living donor liver
272 transplant (LDLT) and those considered for an LDLT but not receiving one. Although
273 the analysis will involve a fairly complex method of matching LDLT recipients with sets
274 of non-recipients, for the purpose of power calculations, we will assume a much simpler
275 2-group design. We anticipate having at least 300 LDLT recipients and 500 non-
276 recipients. Power calculations are based on the (two-sided) logrank test, an exponential
277 survival distribution, and $\alpha=0.05$. Assuming a one-year survival probability of 0.875
278 in the LDLT group, we have 82% power to detect as significant a survival probability
279 among non-recipients as high as 0.83 or as low as 0.91, and 93% power to detect a
280 survival probability among non-recipients as high as 0.82 or as low as 0.92.

281
282 For a comparison of rejection probabilities in the first year after transplant between
283 LDLT (n=300) and cadaveric (n=250) transplants, we assume a two-sided test of
284 binomial proportions with $\alpha=0.05$. We also assume that approximately 32% of
285 cadaveric transplants experienced a rejection episode. We will have 44% power to detect

286 a difference between LDLT and cadaveric transplants if the LDLT proportion is 25%,
287 and 83% power if the LDLT proportion is only 21%.

288 **4.2.5. Statistical Analysis**

289 A comparison of survival between LDLT recipients and those evaluated for LDLT but
290 not receiving a living donor organ will be made. An initial, approximate analysis
291 comparing these groups will use Cox regression, with the time axis starting at time of
292 donor evaluation, a time-dependent covariate for LDLT transplantation, and covariate
293 adjustment for age, gender, race, calendar year of initial evaluation, liver disease etiology
294 and severity, comorbidities and other variables. This analysis assumes that most
295 candidates evaluated for LDLT either receive the transplant or do not receive it due to
296 problems with the donor. In particular, it assumes that non-progression to LDLT due to
297 cadaveric transplantation or because the recipient becomes too sick to transplant is rare.
298 These assumptions can be evaluated when the data are available.

299
300 A second, more difficult but preferred analysis will be performed to compare survival
301 from the time of LDLT surgery among LDLT recipients to a set of controls who were

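### The HCC survival comparison starts at donor evaluation but groups patients by later receipt of LDLT, and its ablation covariate and explant exclusion also use information from after that start

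*Protocol*

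**What the plan says.** - **Time zero and groups (Protocol 3.4.1).** The aim is "To compare the outcomes for patients with HCC from the time of LDLT donor" "evaluation for those receiving LDLT versus those not receiving LDLT. Outcomes" include ablation: those "considered will include survival, hospitalizations, ablative treatments, and HCC" status or recurrence.
- **Controls (4.4.1).** These are HCC patients who had a "donor evaluated for possible LDLT but who did not receive a LDLT. The analysis will" "adjust for cirrhosis etiology diagnosis, center, age, CTP/MELD score, use of ablation" before transplant, and also for the ablation method. No limit to ablation before donor evaluation is stated.
- **Exclusion (4.4.2).** Patients transplanted with a "preoperative diagnosis of HCC and cirrhosis where no HCC was found at explant" are removed, provided they also have no earlier ablation on record that could explain the absence of tumour.
- **Analysis (4.4.4 and 4.4.5).** Group sizes are put at 75 LDLT and 125 non-LDLT. The difference in recurrence or presence of HCC is estimated between LDLT and non-LDLT patients, and then a comparison "of survival between these two groups will be performed using Cox regression, adjusted" for covariates.
- **Parent cohort (4.1 and 4.2.5).** The comparator is patients who have not had LDLT so far. The first model has its time axis starting at "donor evaluation, a time-dependent covariate for LDLT transplantation, and covariate" adjustment. The preferred second analysis compares each LDLT recipient with controls who were alive and transplant-eligible at the same interval after donor evaluation. Section 4.1 describes the HCC patients as the part of this cohort with HCC at entry.

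**The concern.** Receipt of LDLT is known only some time after donor evaluation. If patients are classified from time zero by whether they eventually received it, nobody in the LDLT group can die during the wait, and every death during a wait is counted among the controls. Section 4.2.5 avoids this for the main mortality analysis. Section 4.4 has the same time zero but neither repeats nor cites that method.

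Two other features of 4.4 also look past time zero. Ablation after donor evaluation is partly a consequence of how long the patient waits, so adjusting for it conditions on something that 3.4.1 treats as an outcome. Explant histology exists only for transplanted patients, so eligibility depends on a later event that all LDLT patients have and only some controls have.

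Section 4.4.4 describes its test as comparing a strategy of LDLT with waiting for a cadaveric organ. A survival comparison with these features does not estimate that contrast.

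**Working it through.** **The plan's own figure.** Section 4.4.4 states 90% power for 10% versus 30% with 75 and 125 patients. Alpha is not given there; two-sided 0.05 is assumed, as for the two-proportion test in 4.2.4.
- Pooled proportion: (75×0.10 + 125×0.30)/200 = 0.225.
- Null SE: √[0.225×0.775×(1/75 + 1/125)] = 0.0610.
- Alternative SE: √[0.09/75 + 0.21/125] = 0.0537.
- Continuity correction: (1/75 + 1/125)/2 = 0.0107.
- z = (0.20 − 0.0107 − 1.96×0.0610)/0.0537 = 1.30, so power is 90.3%.

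The figure reproduces and is not in dispute. It concerns proportions, not the Cox comparison.

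**Direction of the immortal-time bias.** Suppose LDLT has no effect and the death rate is λ throughout. Let a be the LDLT patients' person-time before surgery, b their person-time after it, and c the person-time of the controls. Deaths after LDLT number λb. Deaths before LDLT number λ(a + c), and all of them fall in the control group.
- Grouping by eventual LDLT: ratio = [λb/(a + b)] ÷ [λ(a + c)/c] = [b/(a + b)] × [c/(a + c)]. This is below 1 whenever a > 0.
- Time-dependent LDLT: ratio = [λb/b] ÷ [λ(a + c)/(a + c)] = 1.

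**Size, by simulation under no effect.** Assumptions: exponential survival, with one-year survival of 0.875 (the LDLT value in 4.2.4), 0.83 and 0.70; exponential wait unrelated to prognosis; 34–37% receiving LDLT; censoring uniform from 0.25 to 5 years. Ranges are over the three survival values. Rate ratios use 400,000 patients; the Cox fits use the first 8,000 and are noisier.

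| Assumed median wait | Rate ratio, eventual group | Cox HR, eventual group | Rate ratio, time-dependent |
|---|---|---|---|
| 1 month | 0.89–0.91 | 0.88–0.95 | 0.99–1.00 |
| 2 months | 0.81–0.84 | 0.80–0.87 | 0.99–1.00 |
| 3 months | 0.75–0.79 | 0.78–0.81 | 1.00–1.01 |
| 6 months | 0.63–0.67 | 0.61–0.64 | 1.00–1.01 |

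A second simulation used mean rather than median waits, 42% headed for LDLT and censoring with a mean of 2 years. At 17% annual mortality the Cox HRs were 0.94, 0.86, 0.79 and 0.68 for 1, 2, 3 and 6 months. At 30% they were 0.91, 0.83, 0.77 and 0.67.

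**Reach of the explant exclusion.** Appendix A totals, all diagnoses: 862 candidates, of whom 335 received LDLT, leaving 862 − 335 = 527. Of these, 181 had a cadaveric transplant, 107 had died or been removed, and 239 were still waiting.
- Controls with an explant at the snapshot: 181/527 = 34%.
- If everyone still waiting later had a cadaveric transplant: (181 + 239)/527 = 80%.

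The rule can therefore reach every LDLT patient but between 34% and at most about 80% of controls. No HCC-specific figures are given.

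**Ablation.** Section 3.4.1 lists it as an outcome, and 4.4.1 lists it as a covariate for the same comparison. Section 4.4.3 records the number and type of ablations but no dates, so events before and after donor evaluation could not be separated from the listed data.

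**The case against.** The strongest reply is that 4.4.5 never says LDLT is a fixed covariate. Section 4.1 calls the HCC patients a subset of the parent cohort, and the main aim in 3.2.1 uses similar receiving-or-not wording with fixed counts (300 and 500) although its analysis is time-dependent. The omission may be only a missing cross-reference, and a separate SAP could supply it. This stands as a limit on certainty. It does not remove the point: 4.4.5 names the groups and the model, and as written they do not fit the time zero in 3.4.1. Nor would carrying over 4.2.5 resolve the ablation covariate or the explant rule.

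It also stands that 4.4.5 calls the initial HCC analysis mainly descriptive, and that Section 9 plans a descriptive HCC paper.

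Three stronger readings are tempting and are not supported:
- A reader might infer that the explant rule clears all false-positive HCC from the LDLT group. It does not: patients with a recorded ablation are spared, so some can remain in either group.
- A reader might infer from Appendix A that two-thirds of controls (346/527 = 66%) never reach transplant and so have no meaningful pre-transplant ablation history. That is an all-diagnosis snapshot in which 239 of the 346 were still waiting. Ablation can also be recorded for an untransplanted patient; the problem is its timing relative to donor evaluation.
- A reader might infer that all three features favour LDLT. Only the grouping by eventual LDLT has a direction that can be shown.

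**Conclusion.** The point holds, as a should-fix. Followed as written, the HCC survival comparison is biased towards LDLT, with a null hazard ratio of about 0.9 at a 1-month wait and about 0.65 at 6 months. The direction follows from the grouping whenever there is any wait. The size rests on assumed waits and mortality, a constant hazard, and a wait unrelated to prognosis.

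The ablation adjustment conflicts with the outcome list in 3.4.1, and the explant exclusion conflicts with the HCC-at-entry subset in 4.1. The direction and size of bias from these two cannot be determined from the protocol.

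The point does not extend to the main mortality analysis, which 4.2.5 handles correctly. Nor does it extend to the LDLT-versus-cadaveric comparison in 3.4.2 if that clock starts at transplant, because explant findings and earlier ablation are then available in both groups.

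**What to change.** - **4.4.5:** state that the HCC survival comparison uses the time-dependent or matched-control method of 4.2.5. Donor-evaluation, transplant and death dates are already collected under 4.2.3.
- **4.4.2:** for the donor-evaluation analysis, define the cohort by HCC diagnosed at entry, in line with 4.1. Apply the explant exclusion only in the LDLT-versus-cadaveric analysis.
- **4.4.1:** adjust only for ablation before donor evaluation, and keep later ablation as an outcome.
- **4.4.3:** add the date of each ablation, without which the change to 4.4.1 cannot be carried out.

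The cost is wording in three subsections plus one extra chart-abstraction field, best added before abstraction begins. A few explant-negative patients will stay in the donor-evaluation HCC cohort; they would have been classified as HCC when the LDLT decision was made.
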